### **5.2 Exclusion Criteria**

1. If the patient is currently receiving ESA (for example, erythropoietin) with plans to continue during study: Less than 2 months duration of ESA therapy prior to starting study drug and no dose escalation within 2 months of start of study drug.
2. If the patient is being treated with GCSF and/or a TPO-mimetic (for example, Eltrombopag or Romiplostim) with plans to continue during the study: Less than 2 months duration of GCSF or the TPO-mimetic treatment prior to starting study drug; or GCSF and/or TPO-mimetic has been added to ESA therapy within 2 months of start of study drug.
3. If patient is being treated with Lenalidomide with plans to continue during the study: Stable dose for less than 3 months prior to start of study drug.
4. If patient is being treated with HMA (for example, Azacitidine or Decitabine) with plans to continue during the study: Stable dose for less than 6 months prior to start of study drug.
5. Currently enrolled in, or discontinued within the last 14 days from a clinical trial involving an investigational product or non-approved use of a drug, or concurrently enrolled in any other type of medical research judged not to be scientifically or medically compatible with this study.
6. Presence of  $\geq 10\%$  blast by morphologic examination of bone marrow aspirate or biopsy
7. Platelets  $\leq 50,000$
8. Microcytosis on screening CBC (MCV  $< 81$  fL)
9. Active GI ulceration or hemorrhage
10. Have a serious preexisting medical conditions that, in the opinion of the investigator would preclude participation in the study (for example a GI disorder causing clinically significant symptoms such as nausea, vomiting, and diarrhea, or malabsorption syndrome) or that would result in a life expectancy of less than 1 year
11. Known hypersensitivity to deferasirox
12. History of non-transfusional hemosiderosis
13. Prior hematopoietic stem cell transplant for the diagnosis of MDS
14. A second primary malignancy that in the judgment of the principal investigator (PI) or designee may affect the interpretation of results
15. Have an active fungal, bacterial, and/or known viral infection including human immunodeficiency virus (HIV) or viral (A, B, or C) hepatitis
16. Currently using aluminum-containing antacid products
17. History of clinically significant auditory or ocular toxicity with ICT

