## **6.0 SUBJECT REGISTRATION**

Patients will be recruited to participate in this clinical trial during the regular clinical visits of co-investigators. Patients will be given a copy of the consent form for this trial and will have ample time to review the study. The study will be reviewed with the patient by an experienced co-investigator in detail. Patients will be provided with a signed copy of the consent form. Following the signature of a consent form the FHCRC Research Subject Registration Form (**Appendix D**) will be completed and sent to the FHCRC Research Coordinator along with a copy of the signed consent form and protocol specific HIPAA form. The original consent form will remain in the patient's chart. Once this form has been received and screening has been completed, the eligibility checklist (**Appendix E**) will be completed by study staff. The eligibility checklist must be signed by the PI or designee prior to the start of treatment with deferasirox. Ineligible patient will be considered a screen failure and will not be enrolled; however, they may be reconsidered for enrollment at a later date. Patients must be consented prior to any screening procedures and

must be re-consented with each subsequent attempt at screening. An eligibility checklist must be completed with each screening attempt.

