##### 7.5.1 Permitted Concomitant Therapy

1. All study participants will be allowed, as medically justified, access to RBC and platelet transfusions. Concurrent use of an ESA will be allowed if the patient has been on a stable dose for two months prior to screening and continuation of ESA is medically justified. Combination therapy with a TPO-mimetic (such as Eltrombopag or Romiplostim) and/or G-CSF is allowed as long as the patient has been on a stable dose for two months prior to screening. G-CSF will be allowed in the setting of an acute infection if medically justified. Lenalidomide concurrent use is allowed if they have been on a stable dose for at least 3 months of duration. HMA concurrent use is allowed if they have been on a stable dose for at least 6 months.

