**B. Exclusion criteria: Each of the following questions must be marked no for the patient to be eligible**

1. Yes  No  If the patient is currently receiving ESA (for example, erythropoietin) with plans to continue during study: Less than 2 months duration of ESA therapy prior to start of study therapy and no dose escalation within 2 months of start of study therapy.
2. Yes  No  If the patient is being treated with GCSF and/or a TPO-mimetic (for example, Eltrombopag or Romiplostim) with plans to continue during the study: Less than 2 months duration of GCSF or the TPO-mimetic treatment prior to start of study therapy; or GCSF and/or TPO-mimetic has been added to ESA therapy within 2 months of start of study therapy.
3. Yes  No  If patient is being treated with Lenalidomide with plans to continue during the study: Stable dose for less than 3 months prior to start of study therapy.
4. Yes  No  If patient is being treated with HMA (for example, Azacitidine or Decitabine) with plans to continue during the study: Stable dose for less than 6 months prior to start of study therapy..
5. Yes  No  Currently enrolled in, or discontinued within the last 14 days from a clinical trial involving an investigational product or non-approved use of a drug, or concurrently enrolled in any other type of medical research judged not to be scientifically or medically compatible with this study

6. Yes  No  Presence of ≥10% blast by morphologic examination of bone marrow aspirate or biopsy
7. Yes  No  Platelets ≤ 50,000
8. Yes  No  Presence of microcytosis on screening CBC (MCV < 81 fL)
9. Yes  No  Active GI ulceration or hemorrhage
10. Yes  No  Have serious preexisting medical conditions that, in the opinion of the PI or designee would preclude participation in the study (for example a GI disorder causing clinically significant symptoms such as nausea, vomiting, and diarrhea, or malabsorption syndrome)
11. Yes  No  Known hypersensitivity to deferasirox
12. Yes  No  History of non-transfusional hemosiderosis.
13. Yes  No  Prior hematopoietic stem cell transplant for the diagnosis of MDS
14. Yes  No  A second primary malignancy that in the judgment of the PI or designee may affect the interpretation of results
15. Yes  No  Have an active fungal, bacterial, and/or known viral infection including human immunodeficiency virus (HIV) or viral (A, B, or C) hepatitis
16. Yes  No  Currently using aluminum-containing antacid products

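### ESA exclusion 1 (Section 5.2) and checklist item B1 are mis-joined: read literally, neither excludes a patient whose ESA dose was raised within 2 months of study drug

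*Combined protocol and SAP*

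**What the plan says.** Section 5.2 item 1 applies to patients on an ESA who plan to continue it. The excluding condition is "Less than 2 months duration of ESA therapy prior to starting study drug and no dose escalation within 2 months" of study drug.

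Appendix E turns this into checklist item B1: "Less than 2 months duration of ESA therapy prior to start of study therapy and no dose escalation within 2 months" of study therapy. The instruction above the list is "Each of the following questions must be marked no for the patient to be eligible". Section 6.0 makes the form a gate to treatment: "The eligibility checklist must be signed by the PI or designee prior to the start of treatment with deferasirox".

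Section 7.5.1 gives a separate rule for concomitant use: "Concurrent use of an ESA will be allowed if the patient has been on a stable dose for two months prior to screening", provided continuation is medically justified.

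Two neighbouring exclusions are built differently. Item 2 (G-CSF and TPO-mimetics) adds its second disqualifying condition with 'or': "or GCSF and/or TPO-mimetic has been added to ESA therapy within 2 months of start of study drug". Item 3 (lenalidomide) names the disqualifying state directly: "Stable dose for less than 3 months prior to start of study drug".

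**The concern.** An exclusion criterion should list states that disqualify. Item 1 lists one disqualifying state (under 2 months of ESA) and one acceptable state (no escalation) and requires both. Taken at its word, a patient who began an ESA five weeks ago is excluded if the dose was left alone but passes if it was raised. An established user whose dose went up last week also passes.

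This matters because of what the trial measures. The primary endpoint (Section 4.2.1) is erythroid improvement in one open-label arm, tested in Section 15.0 against a fixed 5% null with success at 4 of 25. An ESA escalation shortly before Day 1 is another possible cause of that endpoint, and there is no control arm to reveal it. The stability conditions in items 1 to 4 are the eligibility protection against such confounding, and the one for the agent that acts on the erythroid line does not work as worded.

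**Working it through.** **Logic of item 1 and B1.** Let D be ESA duration under 2 months and E be escalation within 2 months of study drug. As written, a patient is excluded if D and not E. The evident intent is D or E.

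| D | E | As written | Intended |
|---|---|---|---|
| yes | no | excluded | excluded |
| yes | yes | passes | excluded |
| no | yes | passes | excluded |
| no | no | passes | passes |

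The literal rule excludes 1 of the 4 cases and the intended rule 3 of 4. The two cases that differ are the two with an escalation. No other inclusion or exclusion item, in 5.2 or on the checklist, addresses a recent ESA escalation.

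**What 7.5.1 covers.** It requires two stable months before screening. Section 7.3 lets screening open on Day -29. Taking two months as 60 days and screening on Day -29, the dose must be unchanged from Day -89 (-29 - 60) up to screening. An escalation in that stretch bars continued ESA use whatever 5.2 says. An escalation after screening and before Day 1, a window of up to about 4 weeks, breaches neither 7.5.1 nor item 1 as worded.

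**Possible effect on the test.** Section 15.0 states a type I error of 0.0336 and power of 0.9008. The exact single-stage binomial for 4 or more of 25 gives 0.0341 at a rate of 0.05 and 0.9038 at 0.25. The small difference is not part of this point; 0.0341 is the reference below.

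Suppose deferasirox is inactive, k of the 25 patients were recently escalated and respond with probability q because of the ESA, and the rest respond at 0.05. The number of responses is then Bin(k, q) + Bin(25 - k, 0.05). Neither k nor q is in the documents; both are assumptions. P(4 or more) is:

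| k | q = 0.1 | q = 0.2 | q = 0.3 | q = 0.4 |
|---|---|---|---|---|
| 0 | 0.0341 | 0.0341 | 0.0341 | 0.0341 |
| 1 | 0.0384 | 0.0470 | 0.0556 | 0.0642 |
| 2 | 0.0430 | 0.0630 | 0.0857 | 0.1111 |
| 3 | 0.0480 | 0.0822 | 0.1247 | 0.1760 |

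For example, with k = 2 and q = 0.4: 0.36 × 0.0258 + 0.48 × 0.1052 + 0.16 × 0.3206 = 0.1111, where the second factors are the chances of at least 4, 3 and 2 responses among the other 23. The probability passes 0.05 at q of about 0.235 for k = 1, 0.136 for k = 2 and 0.106 for k = 3.

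**The case against.** The strongest reply is that the protocol must be read as a whole. Nothing says 5.2 overrides 7.5.1, so both apply, and 7.5.1 already bars continued ESA after an escalation in the two months before screening. That stands. A reader might infer from item 1 that the trial as a whole accepts any recently escalated ESA user; the documents do not support that, because only the interval from screening to Day 1 is left open by both rules. It does not dispose of the point, since the checklist completed for each patient carries the faulty wording and no stable-dose item.

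Second, the intent is easy to recover, and an investigator is unlikely to apply so odd a rule literally. Also true: only the escalation clause is inverted, and the two unescalated cases come out as intended. Even so, a yes/no item that mixes disqualifying and acceptable states invites inconsistent answers.

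Third, item 2 is not a fully clean model. Its 'or' is right, but it does not test dose stability for G-CSF or TPO-mimetics, which 7.5.1 does require. The comparison shows how the conditions should be joined and no more.

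Fourth, the effect may be slight. Section 2.2 says ESA benefit is mostly confined to patients with lower erythropoietin levels and little transfusion need, whereas the transfusion criterion in Appendix G needs a fall of at least 4 units per 8 weeks. The plausible route is therefore the hemoglobin rise of 1.5 g/dL. Baseline is taken from the latest pre-treatment laboratory results (Section 12.2) and averaged pretreatment counts (Appendix G), so part of an earlier escalation's effect may already be in it. This lowers the concern without removing it.

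**Conclusion.** Item 1 of 5.2 and item B1 are wrong as worded and contradict 7.5.1 on escalation. It is a drafting slip in an operative eligibility rule and should be corrected. The logical finding needs no assumption beyond reading the text literally.

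A reader might take the table of probabilities as showing that the type I error is inflated. It does not: k and q are assumed, k may be 0, and with a single such patient q would have to exceed about 0.235 before the error rate passed 0.05. The size cannot be determined from the documents and is probably small.

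A reader might also infer that the different time anchors (study drug in 5.2, screening in 7.5.1) are a second contradiction. They are not: a patient must meet both, and the stricter one governs.

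**What to change.** In Section 5.2 item 1 and Appendix E item B1, make the excluding condition: *less than 2 months of ESA therapy, OR any ESA dose escalation within 2 months, before start of study drug*. Being tied to study drug, this also closes the interval between screening and Day 1.

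Leave the screening anchor in 7.5.1 as it is. Moving it to study drug would loosen eligibility: with screening on Day -29 and 60-day months, unescalated patients who began an ESA from Day -88 to Day -60 (29 days) are now barred by 7.5.1 and would become eligible.

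The change alters two sentences and leaves the sample size and the 4-of-25 rule untouched. Its cost falls on recently escalated candidates, who must wait until two months have passed. Any already screened may have to start again, since under Section 6.0 patients "must be re-consented with each subsequent attempt at screening. An eligibility checklist must be completed with each screening attempt", and Section 12.2 requires repeat tests once 30 days have elapsed. The documents do not say how many this would affect. The rewording does not address ESA escalation after Day 1, on which 7.5.1 sets no explicit limit.

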### 12.2 Method and Timing

All patients will be screened for eligibility following consent. Screening must be completed within 30 days of start of therapy. If the time period between screening assessments and start of therapy is greater than 30 days then screening tests must be repeated. The most recent screening labs prior to start of therapy will be considered the

baseline assessment upon which response by the modified IWG criteria will be based. Screening assessments will consist of CBC with differential, ferritin, hepatic and renal function tests and a bone marrow aspirate or biopsy. Women of child bearing potential must have a urine or serum pregnancy test performed within 7 days of start of deferasirox.

Follow up tests will consist of monthly CBC with differential, monthly ferritin levels, and monthly renal and hepatic function tests while the patient remains enrolled in the trial. Bone marrow aspiration or biopsy will be repeated at 3 months and 6 months following the start of deferasirox, and as clinically indicated. If at any point a patient is suspected to have disease progression, a bone marrow biopsy or aspirate may be obtained to document this progression. Physical exams and detailed history will be obtained on a monthly basis to screen for potential toxicities. The primary endpoint of hematologic improvement in the erythroid lineage will be assessed at 6 months following start of deferasirox. The secondary endpoints of hematologic improvement in granulocytes and platelets will also be assessed at 6 months. At the end of 6 months patients who do not respond will be offered the option of alternative treatment options including enrollment into clinical trials if possible.

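### Growth-factor run-in: section 5.2 and the checklist count from first dose, section 7.5.1 counts from screening, and the G-CSF/TPO-mimetic item does not test for a dose change

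*Combined protocol and SAP*

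**What the plan says.** Three places in the protocol govern growth factors that a patient brings into the study.

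- **Section 5.2, item 2 (G-CSF, TPO-mimetic).** The first limb excludes "Less than 2 months duration of GCSF or the TPO-mimetic treatment prior to starting study drug". The second limb excludes cases where "GCSF and/or TPO-mimetic has been added to ESA therapy within 2 months of start of study drug". Neither limb mentions a change of dose.
- **Section 5.2, item 1 (ESA).** The item combines a duration of under two months with an escalation clause: "prior to starting study drug and no dose escalation within 2 months of start of study drug".
- **Appendix E, B1 and B2.** These repeat items 1 and 2; B2 reads "Less than 2 months duration of GCSF or the TPO-mimetic treatment prior to start of study therapy". Section 6.0 makes this form the entry gate: "The eligibility checklist must be signed by the PI or designee prior to the start of treatment with deferasirox".
- **Section 7.5.1.** G-CSF and/or a TPO-mimetic "is allowed as long as the patient has been on a stable dose for two months prior to screening". The ESA rule there also requires a stable dose for two months counted back from screening.

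Neighbouring items show that a dose test was in the drafters' minds. For lenalidomide, item 3 excludes "Stable dose for less than 3 months prior to start of study drug", and item 4 does the same for HMA with six months.

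On timing, section 7.3 runs screening from Day -29 to Day -1, and section 12.2 says "Screening must be completed within 30 days of start of therapy". Section 12.2 takes the most recent screening labs as the baseline for response, and Table 2 asks for a pretreatment CBC within 7 days.

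**The concern.** The trial has no control arm, so any rise in counts after Day 1 is read as the effect of deferasirox. The run-in rules for growth factors are what keep a recent change in co-medication out of that reading. Here they disagree in two ways.

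First, the two-month clock stops at first dose in 5.2 and Appendix E but at screening in 7.5.1. The same patient can satisfy one and fail the other.

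Second, item 2 and B2 ask how long G-CSF or a TPO-mimetic has been given, while 7.5.1 asks whether the dose has been stable. The form that staff sign carries only the duration question and does not refer to 7.5.1. A site that follows the form exactly can admit a patient whom 7.5.1 does not allow on that therapy.

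At stake are mainly the platelet and neutrophil improvement rates (secondary endpoint 2 in section 4.2.2), together with protocol deviations that a correctly completed checklist would not reveal.

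**Working it through.** The plan gives no figure for this point, so there is none to reproduce. The check is date arithmetic and a reading of the criteria side by side. Two months is taken as about 60 days.

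**1. Gap between the anchors.** Screening can precede first dose by 29 days (7.3) or 30 days (12.2). That is the largest difference between the two clocks.

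**2. Anchor example.** A TPO-mimetic is started 62 days before Day 1 and screening falls on Day -29.

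- Therapy at first dose: 62 days. Item 2 and B2 do not exclude.
- Therapy at screening: 62 - 29 = 33 days. Section 7.5.1 is not met.

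**3. What this does to the baseline.**

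- Baseline CBC within 7 days (Table 2): at least 62 - 7 = 55 days on therapy.
- Appendix G averages at least two pretreatment counts taken at least one week apart. If the latest is 7 days before Day 1, the earlier one is at least 14 days before: at most 62 - 14 = 48 days on therapy, and 33 days if it was drawn on Day -29.
- The 8-week (56-day) transfusion reference lies wholly within therapy if it ends at first dose (62 > 56). If it ended at a Day -29 screening, 56 - 33 = 23 of its days would precede the start of therapy. Appendix G describes it as pretreatment, which favours the first reading.

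So the anchor gap hardly moves the latest count; it reaches the baseline mainly through an earlier count in the average.

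**4. Dose-change example.** A patient has taken a TPO-mimetic for a year, the dose is raised 14 days before Day 1, and screening falls on Day -7.

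| Rule | Test | Result |
|---|---|---|
| 5.2 item 2, first limb; B2 | under 2 months of treatment? | no, not excluded |
| 5.2 item 2, second limb; B2 | newly added to ESA within 2 months? | no, not excluded |
| 7.5.1 | stable for 2 months before screening? | no: 14 - 7 = 7 days; not permitted |

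The order of events matters. Had this patient been screened on Day -29, the increase would have come after screening, and 7.5.1 read literally would not catch it either.

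**5. Which endpoints it touches.** Platelets at or below 50,000 are excluded, and Appendix G assesses platelet response only below 100 x 10^9/L. An assessable patient therefore starts between 50 and 100 and needs a rise of 30 x 10^9/L lasting at least 8 weeks, which is 30/100 = 30% to 30/50 = 60% of the starting value. Neutrophil response needs at least a doubling and a rise above 0.5 x 10^9/L from a count below 1.0.

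**6. ESA item 1 read as an exclusion.** It excludes when duration is under two months *and* there was no escalation.

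| ESA history | Under 2 months? | No escalation? | Literal result |
|---|---|---|---|
| 1 year, recently escalated | no | no | not excluded |
| 1 month, escalated | yes | no | not excluded |
| 1 month, not escalated | yes | yes | excluded |

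Read literally, the escalation clause narrows the exclusion. A recently escalated patient is not clearly kept out by item 1 or B1, although 7.5.1 asks for a stable ESA dose.

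**The case against.** The strongest reply is that both rules are in the protocol and can be met together: a patient with a stable dose for two months before screening satisfies 5.2, Appendix E and 7.5.1. No passage says that the checklist overrides 7.5.1, so the patients in both examples remain disallowed on that therapy. This stands. A reader might infer that patients with moving baselines *are* enrolled, or that the weaker rule is the operative one. The documents support only that they *can* be enrolled by staff who follow the signed form.

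Two other strong readings also fail.

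- **A two-month run-in shrinks to one month at the baseline CBC.** The 33 days in the example is time on therapy at screening. Section 12.2 uses the most recent screening labs, Table 2 asks for a CBC within 7 days, and Appendix F schedules another on Cycle 1 Day 1. At the latest count the figure is 55 days or more.
- **The primary endpoint is compromised.** The primary endpoint is erythroid. The missing dose test concerns G-CSF and TPO-mimetics, whose direct endpoints are secondary and carry no hypothesis test in section 15.0. Item 2's second limb already excludes recent addition of these drugs to an ESA. An erythroid route exists through the ESA anchor and the unclear item 1, but the documents give nothing to size it. Any inflated type I error would need an assumed number of affected patients and an assumed background response rate.

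The reply does not remove the conflict itself. The form signed before treatment omits a condition that the protocol imposes elsewhere, and does not point to it.

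**Conclusion.** The inconsistency is real and worth correcting; its consequence is limited. The anchors differ by up to 29 or 30 days, with a small effect on the baseline that arises mainly when an earlier count enters the Appendix G average. The more important gap is the absent dose-change test in item 2 and B2. It lets a recent G-CSF or TPO-mimetic dose change through the signed checklist and could bias the single-arm platelet and neutrophil response rates upward.

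This rests on staff using Appendix E as written without separately applying 7.5.1, and on such patients presenting at all. The documents give no number for either. Sample size, type I error and power are untouched.

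**What to change.** Reconcile section 5.2 items 1-2, section 7.5.1 and Appendix E items B1-B2:

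1. Use one anchor for the two-month period in all three places, and state whether a change between screening and first dose counts.
2. Carry the stable-dose requirement that 7.5.1 already states into item 2 and B2 as an explicit dose-change limb, alongside duration and recent addition to an ESA.
3. Reword item 1 and B1 so that short duration and recent escalation are each clearly handled, consistently with 7.5.1.

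Items 3-4 and B3-B4 need no new anchor: they already test dose, and 7.5.1 sets no competing start point for lenalidomide or HMA.

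The cost is a wording amendment to two sections and one appendix. A few patients on recently started or changed growth factors may wait longer to enter, by up to about a month where only the anchor moves.
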